Table 1. Primary and Secondary Objectives and Endpoints	
Secondary Objectives	Secondary Endpoints
1. To characterize the single-dose PK profile of oral rucaparib after a high-fat breakfast compared to that in the fasted state (Part 1 and Part 3 only)	1. PK parameters C_{max} and AUC (fasted and fed)
2. To evaluate the effects of oral rucaparib on the QT/QTc interval measured by ECG (Part 1 only)	2. Change from baseline in QT/QTc interval
3. To evaluate the safety and tolerability of oral rucaparib (Parts 1, 2, and 3)	3. The incidence of AEs, clinical laboratory abnormalities, and ECG abnormalities
4. To evaluate duration of response in the OC population (Part 2 only)	4. Duration of response per RECIST v1.1.
5. To evaluate antitumor activity of oral rucaparib in various solid tumors (Part 1 and Part 3 only)	5. Response per RECIST v1.1; additional analyses including applicable tumor markers
6. To assess progression-free survival (PFS) in the OC population (Part 2 only)	6. PFS defined as the time to first occurrence of disease progression per RECIST v1.1 or death
7. To evaluate survival (Part 2B only)	7. Overall survival (OS)

Table 2. Exploratory Objectives and Endpoints	
Exploratory Objectives	Exploratory Endpoints
1. To explore the relationship between the PK of oral rucaparib and the potential changes in QT/QTc interval (Part 1 only)	1. QT/QTc interval correlated with plasma concentrations of oral rucaparib
2. To profile circulating metabolites of oral rucaparib at steady state at the RP2D (Part 1 only)	2. Metabolic profile in the Day 15 plasma samples
3. To explore the association between genomic alterations identified in tumor tissue and clinical outcome (Part 1, 2, and 3)	3. Mutational status of BRCA1/2 and other homologous recombination genes. Genomic scarring/ loss of heterozygosity (LOH) assessment in tumor tissue and response by RECIST v1.1 and/or tumor markers (ie, CA-125)

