- ^q = PK sample to be collected any time prior to dosing for Cycles 2, 3, 5, 7, and 9. If dosing is held for toxicity or any other reason, PK sample should still be collected at the end of treatment Cycles 1, 2, 4, 6, and 8.
- ^r = Serum AAG sample to be collected on the same day as the PK sample.
- ^s = Part 2A only
- ^t = Part 2B only. For any patient who discontinued from study treatment for reason other than disease progression or death. To be performed within 7 days prior to the start of every 9 weeks of until radiologically confirmed disease progression, death, or initiation of subsequent treatment. Patients who have been on study at least 18 months may decrease the frequency of tumor scans to every 16 (± 14 days) weeks.
- ^u = All Part 2B patients discontinued from treatment, regardless of reason, should be followed for survival, subsequent therapies, and secondary malignancy every 12 weeks (± 7 days) until death, loss to follow-up, withdrawal of consent from study, or study closure, whichever happens first. Follow-up can be performed via the telephone. Diagnosis of any secondary malignancy requires appropriate documentation (i.e., laboratory and/or pathology reports).

Table 12. Schedule of Dosing, Electrocardiograms, and Pharmacokinetic Sampling, for Part 1 and Part 2 Patients

Procedure and Time Points	Part 1 Food-Effect PK Cohort(s) Only		Part 1 All Cohorts (Unless Otherwise Specified)					Part 2 All Patients			
	Cycle 1							Cycles 2+	Cycle 1		Cycles 2+
	Day -8	Day -7	Day -1	Day 1	Day 8	Day 15	Day 22	Day 1 ^a	Day 1	Day 15	Day 1
Oral Rucaparib Administration ^b		X ^c		X ^d	X	X		X	X	X	X
Plasma PK Samples (Any Time Prior to Dosing, if Applicable)		X		X	X		X	X ^e			X
Plasma PK Sample, Predose						X				X	
Plasma PK Samples, Postdose (15 [±2] min, 30 [±3] min, 1 h [±5 min], 1.5 h [±5 min], 2.5 h [±5 min], 4 h [±15 min], 6 h [±15 min], 8 h [±15 min], 10 h [±30 min], and 24 h [±30 min])		X		X		X					
Duplicate Set of Plasma PK Samples for Metabolite Profiling, Predose (Any Time Prior to Dosing)				(X) ^f							
Duplicate Set of Plasma PK Samples for Metabolite Profiling, Postdose (15 [±2] min, 30 [±3] min, 1 h [±5 min], 1.5 h [±5 min], 2.5 h [±5 min], 4 h [±15 min], 6 h [±15 min], 8 h [±15 min], 10 h [±30 min], and 24 h [±30 min])						(X) ^f					
12-Lead ECGs (in Triplicate, >2 min Apart) (Any Time Prior to Dosing)							X	X	X		X ^g

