9.9 Long-term Follow-up

For Part 2B patients only:

- All Part 2B patients discontinued from treatment, regardless of reason, should be followed for survival, subsequent anti-cancer treatments, and secondary malignancy monitoring every 12 weeks [± 7 days] until death, loss to follow-up, withdrawal of consent from study, or study closure, whichever happens first. Follow-up can be performed via the telephone. Diagnosis of any secondary malignancy requires appropriate documentation (i.e., laboratory and/or pathology reports).
- Tumor scans (using the same methodology as was used at screening) for any patient who discontinued from study treatment for reason other than disease progression or death to be performed within 7 days prior to the start of every 9 weeks until radiologically confirmed disease progression, death, or initiation of subsequent treatment. Patients who have been on study at least 18 months may decrease the frequency of tumor scans to every 16 weeks [± 14 days]

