11.2.4.2.2 Tumor Marker (CA-125) Response Rate Based on GCIG CA-125 Criteria (Part 2)

Only patients with elevated level as baseline will be used for this analysis. The incidence of patients with a response (i.e., at least 50% reduction from baseline which is confirmed at a second post-baseline value) in tumor marker CA-125 will be summarized. The time to CA-125 may also be summarized with Kaplan-Meier methodology where the time to CA-125 is defined as duration between the date of first study drug to the date of the first CA-125 response value (at least 50% reduction). If the patient does not have a response they are censored at the last date of cancer antigen measurement.

11.2.4.2.3 *Progression-free Survival (PFS) (Part 2)*

PFS will be calculated as 1+ the number of days from the date of first dose of study drug to disease progression or death, due to any cause, whichever occurs first. Patients without a documented event of progression will be censored on the date of their last adequate tumor assessment (i.e., radiologic assessment) or date of first dose of study drug if no tumor assessments have been performed. PFS will be summarized using Kaplan-Meier methodology.

11.2.4.2.4 *Duration of Response - Secondary Endpoint (Part 2)*

Duration of response for CR and PR, a secondary endpoint in Part 2, will be measured from the date that any of these best responses is first recorded until the first date that PD is objectively documented. Duration of response will be summarized using descriptive statistics (N, mean, standard deviation, median, minimum, and maximum) as well as categorically.

11.2.4.2.5 *Overall Survival (Part 2B)*

Overall survival is defined as the 1+ the number of days from the date of first dose of study drug to death, due to any cause. Patients without a documented event of death will be censored on the date of their last visit. Overall survival will be summarized using Kaplan-Meier methodology time from randomization until death from any cause, and is measured in the intent-to-treat population.

11.2.4.2.6 *Evaluation of Antitumor Activity – Secondary Endpoint (Parts 1 and 3)*

No formal statistical analysis of efficacy will be performed in Part 1. For patients with measurable disease, response to treatment according to RECIST Version 1.1 will be reported via descriptive statistics by dose level.

11.2.4.2.6.1 *Changes in Tumor Markers Applicable to Patient's Tumor Type (Part 1 and 3)*

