Progressive Disease	At least a 20% increase in the sum of the LD of target lesions, taking as reference the smallest sum on study (this includes the baseline sum if that is the smallest on study). In addition to the relative increase of 20%, the sum must also demonstrate an absolute increase of at least 5 mm. The appearance of one or more new lesions is also considered progression.

Evaluation of Nontarget Lesions

Complete Response	Disappearance of all nontarget lesions and normalization of tumor marker level.
Stable Disease/Incomplete Response	Persistence of one or more nontarget lesion(s) or/and maintenance of tumor marker level above the normal limits.
Progressive Disease	Appearance of one or more new lesions and/or unequivocal progression of existing nontarget lesions.

If tumor markers are initially above the institutional ULN, they must normalize for a patient to be considered a complete responder.

Evaluation of Best Overall Response

The best overall response is the best response recorded from the start of the treatment until disease progression/recurrence (taking as reference for PD the smallest measurements recorded since the treatment started). The patient's best response assignment will depend on the achievement of both measurement and confirmation criteria.

Evaluation of Best Overall Response (Patients with Target (+/-Non-target) Disease.			
Target Lesions	Nontarget Lesions	New Lesions	Overall Response
CR	CR	No	CR
CR	Non-CR/non-PD	No	PR
CR	Not evaluated	No	PR
PR	Non-PD or not evaluated	No	PR
SD	Non-PD or not evaluated	No	SD
Not Evaluated	Non-PD	No	NE
PD	Any	Yes or No	PD
Any	PD	Yes or No	PD
Any	Any	Yes	PD
NE = Not evaluable.			

Patients with a global deterioration of health status requiring discontinuation of treatment without objective evidence of disease progression at that time should be classified as having symptomatic deterioration. Every effort should be made to document the objective progression, even after discontinuation of treatment.

In some circumstances, it may be difficult to distinguish residual disease from normal tissue. When the evaluation of CR depends on this determination, it is recommended that the residual lesion be investigated (fine needle aspiration/biopsy) prior to confirming the CR status.

Confirmatory Measurement/Duration of Response

Confirmation

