### 11.2 Secondary Efficacy Endpoints

Secondary efficacy variables include:

- Characterize PK after a high-fat meal compared to the PK in a fasted state (Food effect) (Part 1 and Part 3 only). The PK analysis, including the analysis plan, will be included in the separate PK report as mentioned above, thus no further information around food effect will be included here.
- Evaluate the effects of oral rucaparib on  $Q_t/Q_{Tc}$  intervals by ECG (Part 1 only). A separate analysis plan and report based on this objective has been completed. Thus, no further info around this endpoint will be included here.
- Safety and tolerability as further detailed in section 14
- Duration of response in Ovarian Cancer patients (Part 2A and 2B only)
- Evaluate antitumor activity in various solid tumors (Objective Response in Part 1 and Part 3)
- Progression-Free Survival (PFS) in the Ovarian Cancer population (Part 2 only)
- Overall Survival (Part 2B only)

- ORR per RECIST v 1.1 and Gynecologic Cancer Intergroup (GCIG) CA-125 criteria in the Ovarian Cancer Population (Part 2 Only)

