### 12.2.2 Duration of Response (Part 2A and Part 2B)

Duration of response (DOR) for any confirmed RECIST CR or PR will be measured from the date of the first occurrence of a response until the first occurrence of PD per RECIST. DOR will be summarized as a time to event variable. For patients who continue treatment post-progression, the first date of progression will be used for the analysis. Any patients with an ongoing response will be censored at the date of the last post-baseline scan. The Kaplan-Meier methodology will be used to summarize DOR. If able to be estimated, the 50th (median) together with a 95% Confidence Interval (CI), will be presented. The number of patients with PD events and the number of censored patients will also be presented.

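### PFS and duration of response share one rule across Parts 2A and 2B, but scheduled scans after the end-of-treatment visit and survival contact after day 28 exist only for Part 2B

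*Protocol*

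**What the plan says.** **Endpoints.** Protocol 4.1 (Table 1) sets a secondary objective for all of Part 2: "To assess progression-free survival (PFS) in the OC population". DOR is a secondary endpoint for the same population, and SAP 11.2 names Parts 2A and 2B for it. Protocol 11.2.4.2.3 and SAP 12.2.1 count PFS from first dose to "disease progression or death, due to any cause, whichever occurs first". DOR in SAP 12.2.2 ends at RECIST progression only.

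**Censoring.** PFS without an event is censored at the last adequate tumor assessment. For DOR: "Any patients with an ongoing response will be censored at the date of the last post-baseline scan". Both rules apply to both cohorts, and SAP 13.1 allows no imputation.

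**Follow-up.** Table 11 serves both cohorts, but its long-term follow-up column does not. Nine-weekly scans carry footnote t: "Part 2B only. For any patient who discontinued from study treatment for reason other than disease progression or death". Twelve-weekly contact for survival, later therapy and second malignancy (footnote u) is also for Part 2B. Section 9.9 opens "For Part 2B patients only", and 9.10.5.1 repeats the limit for scans. For Part 2A the last scheduled scan is at the end-of-treatment visit (9.7, 9.10.5.1) and the last contact is the 28-day adverse-event visit (9.8). Deaths within 28 days of the last dose are reported as SAEs (10.2).

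**A general instruction.** For patients who stop for symptomatic deterioration without objective progression, Appendix A says: "Every effort should be made to document the objective progression, even after discontinuation of treatment". No Part 2A visit or scan schedule carries this out.

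**The concern.** The Kaplan-Meier estimate is unbiased only if patients censored at a given time have the same outlook as those still followed. Patients who stop for toxicity, intercurrent illness, symptomatic deterioration or by request may not. In Part 2A they leave observation at about the time they stop. In Part 2B they are still scanned, at least until a new treatment begins, and their deaths are sought until the end of the study.

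Two things are at stake. First, the Part 2A PFS and DOR estimates may be too long. Secondly, Part 2A and Part 2B results will appear under the same label although they were observed differently. Protocol 3.3 encourages reading them together: it describes the cohorts as similar apart from the number of prior lines, and presents Part 2 as a whole as the evaluation of efficacy.

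**Working it through.** **1. What is observed after a stop without progression.**

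| | Part 2A | Part 2B |
|---|---|---|
| End-of-treatment scan | yes | yes |
| Later scans | none scheduled | every 9 weeks until progression, death or subsequent treatment |
| Deaths up to day 28 | captured as SAEs | captured |
| Deaths after day 28 | no planned capture | 12-weekly contact |
| PFS and DOR censoring rule | last scan | last scan |

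The missing deaths matter for PFS only, because DOR in the SAP has no death component and OS is a Part 2B endpoint. PFS is not censored at new therapy in either document. A late Part 2B death found by telephone can therefore be a PFS event, while the same death in Part 2A would go unseen.

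**2. Size for PFS.** The plan states no PFS figure to reproduce. Every input here is an assumption except n = 41 (Protocol 6.1).

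- On-treatment PFS is exponential with median 9 months: h = ln 2 / 9 = 0.0770 per month.
- A fraction f of patients stop before progression, at constant hazard g = h·f/(1−f).
- After stopping, the progression hazard is k·h.
- There is no administrative censoring, and censoring falls at the stop.

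Part 2A rule: the Kaplan-Meier curve follows h alone, so the median is 9.0 months whatever f and k are.

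Full follow-up: with x = h·t and a = 1/(1−f),
S = e^(−a·x) + [f/(1−f)]·[e^(−k·x) − e^(−a·x)]/(a − k).
For f = 0.20 and k = 2, a = 1.25 and S = (4/3)e^(−1.25x) − (1/3)e^(−2x). At t = 8.46 months, x = 0.651 and S = 0.591 − 0.091 = 0.50. The median is 8.5 months.

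Stops counted as events: the total hazard is h/(1−f), so the median is 9(1−f).

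| f (about, of 41) | Part 2A rule | Full follow-up, k = 1 / 2 / 3 | Excess, k = 1 / 2 / 3 | Stops as events |
|---|---|---|---|---|
| 10% (4) | 9.0 | 9.0 / 8.7 / 8.6 | 0 / 0.3 / 0.4 | 8.1 |
| 20% (8) | 9.0 | 9.0 / 8.5 / 8.1 | 0 / 0.5 / 0.9 | 7.2 |
| 30% (12) | 9.0 | 9.0 / 8.2 / 7.7 | 0 / 0.8 / 1.3 | 6.3 |

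**3. Gap to Part 2B.** Full follow-up is not what Part 2B does, since footnote t ends scanning at subsequent treatment. Suppose, as a further assumption, that new treatment starts 2 months after stopping, and ignore later deaths. With f = 20%, a simulation under the Part 2B scan rule gives medians of about 8.7 months (k = 2) and 8.5 months (k = 3). The gap to the Part 2A rule is then 0.3 and 0.5 months.

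**4. Against sampling error.** In simulated cohorts of 41 with f = 20%, the Part 2A median has a standard error of about 2.2 months.

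DOR was not simulated. The direction is the same, but its size is unquantified.

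**The case against.** Several points on the other side stand.

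- A reader might infer that Part 2A has no imaging once treatment stops. It has the end-of-treatment scan, and deaths to day 28 are captured.
- A reader might infer that a first response seen just before stopping cannot be confirmed in Part 2A. SAP 12.1 needs a later assessment at least 28 days on, and the end-of-treatment scan can supply it. The gap is limited to responses first seen less than 28 days before that scan. It is narrower still because 9.10.5.1 requires a confirmatory scan 4-6 weeks later for responses first seen at Cycle 7 or beyond. Where it remains, it works against Part 2A.
- A reader might infer that the plan rests on a flawed comparison of 2A with 2B. SAP section 4 reports the cohorts separately without pooling, and no comparison is specified. Both endpoints are secondary and descriptive.
- The bias is modest against a standard error of about 2.2 months, and its inputs are assumed. Protocol 3.2.2.1 reports that none of the ovarian cancer patients treated at the Phase II dose had stopped for a treatment-related adverse event as of November 2014, which favors the low end.
- Counting stops as events is no better as an estimate. With f = 20% and k = 2 it gives 7.2 against 8.5, an error of −1.3 months; the current rule errs by +0.5.

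None of this removes the difference in follow-up. Separate reporting does not make the Part 2A median unbiased, a wide interval does not correct a shift, and neither document mentions the difference or plans a check.

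**Conclusion.** The point holds as a limited one. One endpoint definition is applied to two follow-up schedules. In Part 2A, progression after the end-of-treatment visit and deaths after day 28 have no planned capture. Part 2A PFS and DOR may therefore be too long, and they are not measured in the same way as in Part 2B.

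The direction depends on patients who stop without progression doing worse than those who continue; if they do not, the bias is zero. Under the assumed 9-month median, 10-30% stopping and hazard ratio of 1 to 3 after stopping, the PFS median is too long by 0 to about 1.3 months against full follow-up, and by less against Part 2B. The documents do not support saying that the Part 2A medians are in fact inflated, because they give neither a stop rate nor outcomes after stopping.

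**What to change.** Change SAP 12.2.1 and 12.2.2 only:

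1. State that Part 2A tumor follow-up ends at the end-of-treatment visit and that death capture ends 28 days after the last dose.
2. Tabulate, by cohort and reason, the patients censored after stopping treatment without progression.
3. Add a Part 2A sensitivity analysis of PFS and DOR that counts such stops as events. Label it a conservative lower bound and not a replacement estimate.
4. Report Part 2B PFS and DOR a second time under the Part 2A follow-up rule: scans through the end-of-treatment visit and, for PFS, deaths through 28 days after the last dose. This gives a like-for-like reading beside the planned Part 2B analysis, which stays as it is.

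All of this uses data already collected. The cost is a table, a few Kaplan-Meier runs, and a published lower bound that could be clearly less favorable: 7.2 against 9.0 months in the 20% example. If the table shows few such stops, it settles the matter. Counting stops as events should not become the common rule for both cohorts: it would overcorrect and discard the post-treatment scans of Part 2B. New telephone follow-up for Part 2A is not proposed. It would need a protocol amendment, and deaths recorded without scans would enter PFS late, after unseen progression.

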9.7 End-of-Treatment Visit (Parts 1-3)

The following procedures will be performed for all patients after the last dose of oral rucaparib:

- Physical examination
- Weight
- ECOG performance status
- Vital signs
- Concomitant medications since last visit
- ECGs (in triplicate >2 min apart)
- Hematology and serum chemistry (including lipid panel)
- Serum pregnancy test for women of childbearing potential
- Urinalysis (Part 3 only)
- Tumor marker(s) (optional for all patients in Part 1; in Part 2 CA-125 required for all patients and in Part 3, appropriate markers according to tumor type e.g., CA-125 or CEA are collected). *(Note: tumor marker data will be collected retroactively for all Part 1 patients who were enrolled under other protocol versions).*
- Serum pregnancy test for women of childbearing potential
- Tumor scans (using the same methodology as was used at screening). Tumor scans to be collected and stored for possible evaluation by independent radiology review *(for Part 2A, Part 2B, and Part 3 patients)*
- Tumor tissue sample – archival and/or fresh biopsy. Refer to the Laboratory Manual for detailed sample collection, preparation, and shipment instructions.
 - Part 1, an optional fresh biopsy may be collected at time of disease progression/treatment discontinuation
 - Part 2, an archival tumor tissue sample will be required from all newly enrolled patients and will also be collected from previously enrolled patients who provide appropriate

consent. The sample is not required to be provided before enrollment, but should be submitted as soon as possible after a patient begins treatment. An optional fresh biopsy may be collected at time of disease progression/treatment discontinuation

- Part 3, an optional fresh biopsy may be collected at time of disease progression/treatment discontinuation
- AE monitoring

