9.10.5 Efficacy Evaluations

9.10.5.1 Tumor Assessments

For Part 1 and Part 2, tumor assessments will be performed at screening, within 7 days prior to the start of Cycles 3, 5, and 7, within 7 days prior to the start of every three cycles thereafter, beginning with Cycle 10, and at the end-of-treatment visit.

For Part 2B, tumor assessments will also be performed during the long-term follow-up period for any patient who discontinued from study treatment for reason other than disease progression or death, within 7 days prior to the start of every 9 weeks until radiologically confirmed disease progression, death, or initiation of subsequent treatment. Patients who have been on study at least 18 months may decrease the frequency of tumor scans to every 16 weeks (± 14 days).

For Part 3, tumor scans will be performed at screening, within 7 days prior to the start of Cycles 3, 5, and 7, and within 7 days prior to the start of every three cycles thereafter, beginning with Cycle 10.

If initial CR or PR is noted at Cycle 7 or beyond, confirmatory scans must be performed 4–6 weeks later. Tumor response will be interpreted using RECIST Version 1.1 ([Appendix A](#)).

Tumor assessments should consist of clinical examination and appropriate imaging techniques (preferably CT scans of the chest, abdomen, and pelvis with appropriate slice thickness per RECIST); other studies (MRI, X-ray, PET, and ultrasound) may be performed if required. The same methods used to detect lesions at baseline are to be used to follow the same lesions throughout the clinical study. Investigators should perform scans of the anatomical sites that, in their judgment, are appropriate to assess based on each patient's tumor status. For patients in Part 2 and Part 3, tumor scans will be collected for possible evaluation by independent radiology review.

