12 PATIENT DISPOSITION

12.1 Patient Discontinuations

A patient must be discontinued from protocol-prescribed therapy if any of the following apply:

- Consent withdrawal at the patient's own request or at the request of their legally authorized representative
- Progression of patient's underlying disease
- Any event, adverse or otherwise, that, in the opinion of the investigator, would pose an unacceptable safety risk to the patient
- An intercurrent illness that, in the opinion of the Investigator, would affect assessments of the clinical status to a significant degree and requires discontinuation of therapy
- A positive pregnancy test at any time during the study
- Increase in QT/QTc of >60 msec over baseline or QTc >500 msec

In addition, the sponsor may discontinue the trial early for any of the reasons noted in [Section 13.6](#).

The sponsor (or designee) should be notified of all study terminations as soon as possible. The date and reason for cessation of oral rucaparib must be documented in the eCRF and source documents. To the extent possible, follow-up procedures should be performed on all patients who receive rucaparib. The follow-up visit should occur 28 (± 3) days following the last dose of rucaparib. Patients will be followed for 28 days after the last dose of rucaparib for safety; those with ongoing SAEs will be followed until either resolution or stabilization has been determined.

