### 12.2.1 Progression-free Survival (Part 2)

PFS will be calculated as 1+ the number of days from the date of first dose of study drug to disease progression or death, due to any cause, whichever occurs first. Patients without a documented event of progression will be censored on the date of their last adequate tumor assessment (i.e., radiologic assessment) or date of first dose of study drug if no tumor assessments have been performed. PFS will be summarized using Kaplan-Meier methodology.

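### Part 2B post-treatment scans are not scheduled for patients who stopped for progression that imaging has not shown, which biases PFS and duration of response upward

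*Protocol*

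**What the plan says.** **Who is scanned after treatment (Part 2B).** Protocol Table 11 footnote t, Section 9.9, Section 9.10.5.1 and the Efficacy Assessments row of the synopsis all carry the same condition. Footnote t reads "For any patient who discontinued from study treatment for reason other than disease progression or death", and Section 9.10.5.1 reads "for any patient who discontinued from study treatment for reason other than disease progression or death, within 7 days prior to the start of every" (the interval is 9 weeks). None of the four says radiologic or RECIST.

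**When that scanning ends.** The rule runs "until radiologically confirmed disease progression, death, or initiation of subsequent treatment".

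**Why a patient stops treatment.** Section 12.1 lists "Progression of patient's underlying disease", with no imaging requirement.

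**What everyone gets.** Section 9.7 opens with "The following procedures will be performed for all patients after the last dose of oral rucaparib", and its list includes tumor scans. Section 9.9 adds survival follow-up every 12 weeks for all Part 2B patients, whatever their reason for stopping.

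**After symptomatic deterioration.** Appendix A says: "Every effort should be made to document the objective progression, even after discontinuation of treatment". It attaches no schedule.

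**Endpoints.** The PFS event is RECIST v1.1 progression or death (SAP Table 1). SAP 12.2.1 adds: "Patients without a documented event of progression will be censored on the date of their last adequate tumor assessment". Under SAP 12.2.2, duration of response ends only at RECIST progression, and patients with an ongoing response are censored at the last post-baseline scan.

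**The concern.** The exit from post-treatment scanning is radiologic and the entry is not. A patient whom the investigator takes off treatment for worsening disease has, on a plain reading, stopped for disease progression and falls outside the scheduled scans, even if no scan has shown RECIST progression. From Cycle 7 on, scans are three 21-day cycles (9 weeks) apart, so clinical worsening ahead of the imaging is foreseeable.

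These patients are close to progression. Censoring them at the last scan treats them as if they had the average prognosis of those still at risk. That is informative censoring, and it lengthens both time-to-event secondary endpoints. The SAP has no sensitivity analysis for it: Section 13.1 only refers back to the censoring rule under each endpoint.

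**Working it through.** **1. The plan's own figures.** The documents give no event count, median or power for Part 2B PFS or duration of response. The only Part 2B design figures are the Clopper-Pearson limits for 40 patients. They reproduce: 12/40 gives 16.6-46.5%, 16/40 gives 24.9-56.7% and 20/40 gives 33.8-66.2%. They do not bear on this point.

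**2. Path of one patient.** Take a patient stopped for symptomatic progression.
- The end-of-treatment scan is done. If it shows RECIST progression, the event is recorded and there is no problem.
- If it does not, the four statements of the long-term rule schedule nothing more, and Appendix A asks only for effort.
- Duration of response (if a responder): censored at the last scan. Death is not an event, so survival follow-up does not help.
- PFS: censored at the last scan, or an event at the date of death if death is recorded. The event is then dated later than the unobserved progression.

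**3. Size by formula.** Let q be the share of patients stopped this way and s the probability that the end-of-treatment scan already shows RECIST progression. A share f = q(1 - s) of progression events is replaced by censoring. With exponential times and a short interval from stop to progression, the observed hazard is (1 - f) times the true one, so the Kaplan-Meier median is multiplied by 1/(1 - f):
- q = 5%: 1/0.95 = 1.053 (s = 0); 1/0.975 = 1.026 (s = 50%)
- q = 10%: 1/0.90 = 1.111; 1/0.95 = 1.053
- q = 20%: 1/0.80 = 1.250; 1/0.90 = 1.111

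**4. Size by simulation.** Assumptions, none of them from the documents: exponential time to RECIST progression, RECIST progression 0.2 to 2 months after the stop, data cut at 24 months. Medians in months for a true median of 9; the reference scans every patient to RECIST progression:

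| q | s | Reference | Censored at last scan | Change |
|---|---|---|---|---|
| 5% | 50% | 8.99 | 9.20 | +2% |
| 5% | 0 | 8.99 | 9.43 | +5% |
| 10% | 50% | 8.94 | 9.38 | +5% |
| 10% | 0 | 9.00 | 9.91 | +10% |
| 20% | 50% | 8.91 | 9.83 | +10% |
| 20% | 0 | 9.01 | 11.08 | +23% |

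The percentages are nearly the same for true medians of 6, 8 and 12 months. Widening the interval to 0-3 months gives 9.43, 9.90 and 11.01 for s = 0, and the direction is upward in every scenario.

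**5. PFS with later deaths counted.** Assuming a median survival of 12 months after progression and s = 0, the PFS median is 9.42, 9.89 and 10.90 for q = 5%, 10% and 20%. Recorded deaths remove little of the bias.

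**6. Counting the stop as an event.** In the same s = 0 simulations the median becomes 8.94, 8.90 and 8.80. The upward bias is gone, and what remains is a small shift of 1-2% the other way, because the stop precedes RECIST progression.

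**The case against.** The strongest objection is that Appendix A gives patients who stop without objective evidence of progression a label of their own, symptomatic deterioration. On that view they stopped for a reason other than disease progression and footnote t already includes them. Other text also ties progression to RECIST, for example Section 7.4.4. This shows that the rule is ambiguous, but it does not settle it. The label is a response classification to which the scan rule does not refer. Section 7.4.4 says radiologic progression by RECIST where it means that, and Section 10.1 separates symptomatic progression from progression seen only on imaging. Whether a patient is scanned would depend on how the site codes the stop.

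Several stronger readings are tempting but unsupported:
- *That these patients are never scanned to progression.* The end-of-treatment scan is mandatory for all and may show it.
- *That the schedule prevents documentation.* It omits these scans but does not forbid them, and Appendix A asks for them.
- *That they are always censored for PFS.* A recorded death is an event.
- *That CA-125 rises are an established route to stopping.* CA-125 is measured every cycle, but neither document defines CA-125 progression or makes it a stopping criterion.
- *That the reported median moves by a whole 9-week scan interval.* This depends on the chosen median. With a true median of 8 months, survival at week 36 is 48.8%, so a change of about one point is enough. With 10% affected, medians of 7, 7.5, 8.5 or 9 months show no shift.

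It is also fair that these are descriptive, single-arm summaries on which no hypothesis rests. With 40 patients and a true median of 8 months, sample medians range from about 5.0 to 12.1 months by chance. The bias is smaller than that range, but it is systematic and the confidence interval does not reflect it.

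**Conclusion.** The point stands as a mismatch between the entry and exit conditions of the Part 2B scan rule, with an upward bias in PFS and duration of response. The median is raised by about 2-5% if 5% of patients are affected, 5-10% if 10% (four of 40), and 10-23% if 20%. The lower figure in each pair assumes that the end-of-treatment scan shows RECIST progression in half of these patients, the upper that it shows it in none. All of this rests on an assumed share, exponential times and RECIST progression 0.2 to 2 months after the stop. The direction is firm and the size is not. Confirmed response rate, the primary endpoint, is little affected. The change is worth making but is not critical.

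**What to change.** **Protocol.** In the synopsis, Table 11 footnote t, Section 9.9 and Section 9.10.5.1, change the entry condition to *reason other than radiologic (RECIST v1.1) progression or death*, so that it matches the rule's own end point. The criteria for stopping treatment are untouched.

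**SAP.** In 12.2.1 and 12.2.2, add a sensitivity analysis that counts discontinuation for progression without documented RECIST progression as an event on the stop date. Section 12.1 of the protocol already requires the date and reason for stopping in the eCRF, so no new data are needed. Report the number of such patients beside it, which replaces the assumed share with an observed one.

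**Cost and limits.** The cost is a few words in four places, a few extra scans on the existing 9-week schedule, and one analysis. Scanning would still end when subsequent treatment starts, so the wording recovers only part of the bias. The SAP also describes Part 2B enrollment in the past tense, so the edit may come too late for some patients. The sensitivity analysis is needed for both reasons. It dates the event slightly early, so it should be read beside the main analysis and not replace it.
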